#### 9.5. Potential Benefits

Steroids have been shown to be effective in treating patients with COVID-19 on oxygen and there is also some evidence that other treatments such as the antiviral medicine called Remdesivir may help patients that are severely affected. Early intervention with Favipiravir, has the potential to improve outcomes in those with COVID-19 infection.

## 9.6. Potential Risks

The following are known side-effects of the investigational medical product:

Favipiravir	
Common	Raised uric acid level (4.8%); diarrhoea (2.3%); reduced neutrophil count (1.8%); raised liver enzymes (1.6%); nausea (2.1%); urinary tract infection (1.5%), headache (1.1%), vomiting (1.0%), blood triglycerides increased (1.9%)
Uncommon or Rare	Confusion; fulminant hepatitis; renal failure; agranulocytosis; Steven- Johnson syndrome (toxic epidermal necrolysis)
Cautions	Participants on theophylline, pyrazinamide, repaglinide, or famiciclovir should be treated with caution due to drug interactions

#### 10. PARTICIPANT ASSESSMENTS

#### 10.1. Baseline Data Collection

The following information will be collected:

- Demographics
- Co-morbidities
- Medication history and allergy
- Date of COVID-19 symptom onset
- Date of confirmatory COVID-19 test (SARS-CoV-2 infection by PCR or other National standard)
- Smoking status
- Travel history for preceding 6 months
- Clinical parameters (Heart rate, Respiratory rate, Oxygen Saturations)
- Baseline bloods (Full blood count, C-reactive protein, procalcitonin (if this is not part of site
  routine testing it is not required by protocol), ferritin, urea, d-dimer, LDH, troponin, urea &
  electrolytes, liver function (if available)

#### 10.2. Inpatient Data Collection

Whilst patients are hospitalised all routine data, including laboratory test results, procedures and medication will be collected as necessary, as part of the trial from day 0 to day 28 or until discharge, whichever is sooner. Change in ordinal score lasting >24 hours will be recorded. If patients are readmitted within the 28-day period, data will also be collected from this second admission until 28 days post-study commencement.

## 10.3. Follow-Up Data Collection

For participants discharged prior to day 10, a member of the research team will telephone and conduct a short interviews to collect the following information:

- Study drug compliance Drug accountability data will be collected during the Trial. Any deviation from protocol-directed administration is to be reported.
- AEs and SAEs
- Concomitant medications
- Overall health
- Ordinal score (including at discharge) collected as a snapshot

## 10.4. Sample Collection

Patients will be required to provide research samples at 3 time points whilst on the trial:

Time	Blood	Viral Swab	Sputum	Urine	Serology
(days)					SARS-CoV-19
Baseline	20ml	1 x Nasopharyngeal	As able	10ml	

Between	20ml	1 x Nasopharyngeal	As able	10ml	
Day 5-10					
Between	20ml	1 x Nasopharyngeal	As able	10ml	COVID-19
Day 14-28					antibody test

Participants discharged home before day 5 will be requested to return twice (provided they are well enough), for repeat sampling to be collected between days 5 to 10 and days 14 to 28 post-randomisation. Participants discharged home before day 14 will be requested to return once (provided they are well enough), for repeat samples to be collected between days 14 and 28.

If bronchoscopy is performed on any study participant as part of standard of care, an additional bronchoalveolar lavage sample and endobronchial brushings will be collected for research purposes. If this is the case, an additional paired blood sample will be collected by a member of the clinical or research team and used for research purposes.

For exploratory endpoints it is not required to get all exploratory research samples for all participants. Each site will separately agree with the lead sponsor and this will be based on their capabilities and available resources.

A laboratory manual will be provided to all sites detailing collection, processing and handling procedures. Samples will be stored at -80°C or -150°C at site for batch shipment to agreed locations for interim storage. Samples will then be transferred for pathological, inflammatory and genetic analyses to the agreed laboratories, as detailed within the instructions provided in the lab manual. All sites will have tissue transfer agreements in place prior to the transfer of relevant material.

Collected samples will only be labelled with the participants unique study number. Solely the local study team will have the ability to link the patient identifier back to the participant.

Participants are being asked to consent to their samples being stored for up to 10 years for potential future research and to that storage being outside the EU, if necessary.

## 11. DATA COLLECTION & MANAGEMENT

#### 11.1. Source Documentation

Source documents are an integral part of the trial and evidence the integrity of the data collected. The investigator and institution should maintain adequate, complete and accurate source and study documentation that include all relevant medical information for every participant. Source documents and data should be attributable, legible, contemporaneous, original, accurate, and complete. Where changes to source data are made these changes should be traceable, and not obscure the original entry. An explanation for this change should be available.

All data reported on the eCRF should be transcribed from source documents so must match the source document, where discrepancies are identified these discrepancies must be explained. The investigator and institution must ensure that all previous and current source data is available and that not source data is destroyed during the trial.

For the purposes of the trial and in line with GCP confirmation of consent and or assent, including date of consent and or assent should be documented in the participants' medical notes. Once randomised this information should also be entered into the participants' medical notes, along with their Participant entry, intervention and date of administration of intervention.

## 11.2. Data Collection

All participant data relating to the study will be recorded within participant specific electronic case report forms (eCRF) onto an electronic data capture system unless transmitted electronically (e.g. radiology reports). The investigator is responsible for verifying that the data entered in the eCRF is accurate and correct. The investigator must maintain accurate source data documentation that evidences the information entered in the eCRF. Site staff must not enter any personally identifiable participant information into the eCRF, only the Participant identification number should be used to link the eCRF entry to the participant.

Corrections to eCRF entries can be made, however these will not mask the previous entry and an explanation for the change should be provided. The site should ensure that data is entered into the eCRF within a reasonable timeframe to ensure continual data analysis and safety monitoring. All SAEs are to be reported within 24 hours.

#### 11.3. Access to Data

The investigator and site must allow trial-related enquiries and must make available direct access to source data documents.

Upon Sponsor request the investigator and site will promptly disclose all trial documentation to the Sponsor(s) or regulatory agency for the purposes of monitoring, audits, and regulatory agency inspections.

The investigator and site agree to make reasonable efforts to implement any request that results from the inspection.

#### 11.4. Data Management

The Lead Sponsor is responsible for the data management of the trial, including verification to confirm that:

- eCRF entries are accurate, complete, and verifiable from source documents
- the safety and rights of participants are being protected
- the correct versions of documentation are in use PIONEER Version 2.4 21st April 2021 CONFIDENTIAL

- all site personnel supporting the trial are authorised and delegated to do so.
- the study is being conducted in accordance with the currently approved protocol study agreements, ICH GCP, and all applicable regulatory requirements

Data from the eCRF will be entered into a study specific database by designated staff on a regular basis. The database will be kept securely by the Lead Sponsor and access will be given to authorised personnel only, a log of which will be stored in the Trial Master File.

# 11.5. Any data anomalies or values found to be outside normal ranges will be checked with the Investigator. When corrections are required these will be made on CRF and the study database will be amended. Archiving Data

Following completion of the trial, all trial records and documents, including signed informed consent forms, must be retained by the investigator site for a period no less than 15 years after trial completion unless regulations require a longer retention period.

Records are not to be destroyed without written approval from the lead sponsor.

#### 12. SAFETY REPORTING

#### 12.1. Adverse Events: Definitions and Procedures for Evaluating, and Reporting

All Non-COVID-19 associated AEs and SAEs either observed by the research/clinical team, or reported to the research/clinical team, as well as all actions taken to treat the event must be recorded within the participants medical notes and entered into the eCRF along with the information relating to the duration and severity of the event with the Investigator's opinion of the causal relationship to the treatment (unrelated, unlikely to be related, possible related, probable related, and definitively related).

## 12.2. Adverse Events (AEs) Definition

For the purposes of this study, any non-COVID-19 related untoward medical occurrence, either newly acquired or worsening of a current AE, in a patient or clinical trial participant administered a study intervention whether or not considered related to the study intervention.

An AE can therefore be any unfavourable and unintended non-COVID-19 related sign (including an abnormal laboratory finding), symptom, or disease (new or exacerbated) temporally associated with the use of a study intervention.

Events meeting the AE definition for this study:

- Any non-COVID-19 associated abnormal laboratory test results (haematology, clinical chemistry, or urinalysis) or other safety assessments (e.g., Electrocardiogram, radiological scans, vital signs measurements), including those that worsen from time of consent
- Any non-COVID-19 associated exacerbation of a pre-existing condition including either an increase in frequency and/or intensity of the condition.

- Any new non-COVID-19 associated conditions detected or diagnosed after the study intervention has been administered to the participant.
- Symptoms, or the clinical sequelae of a suspected drug-drug interaction.

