#### 7. TRIAL DESIGN

The study is an open-label, two arm, multi-centre randomised controlled clinical trial, to investigate the clinical effectiveness, safety, and resource utilisation of early treatment intervention in patients admitted to hospital with a suspected or proven COVID-19 infection. Subjects will be randomised 1:1 to one of two arms to receive:

- Arm 1: Favipiravir + standard of care
- Arm 2: Standard of care

The study treatment duration will be 10 days for each participant. If a participant recovers sufficiently to be discharged home before day 10, favipiravir will be supplied and the regimen completed as an outpatient.

Samples will be collected at three timepoints: baseline, between days 5 to 10 and days 14 to 28 (see section 9.4). In such instances where participants recover sufficiently to be discharged home and are not in hospital at the latter sample collection timepoints, they will be invited to return to facilitate this (provided that they are well enough and maximally twice).

For further information on activities at visits and schedule see Section 8.

Participants will exit the study at day 28 or if they become deceased.

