## 12.4. Serious Adverse Events (SAEs) Definition

A serious non-COVID-19 associated adverse event is any untoward medical occurrence that at any dose:

- Results in death
- Is life threatening in the context of "serious" life threatening refers to any event where the participant was at risk of death at the time of the event.
- Requires in-patient hospitalisation or prolongation of existing hospitalisation Hospitalisation for an elective procedure to treat a pre-existing condition which occurred prior to study intervention that has not worsened is not an SAE
- Results in persistent or significant disability/incapacity
- Is a congenital anomaly/ birth defect
- Is another important medical event that may not be immediately life-threatening or result in death or hospitalisation but medical and or scientific judgement has determined the event may jeopardise the participant or may require medical or surgical intervention to prevent one of the other outcomes as listed above. Examples of such events include, invasive or malignant Cancers, intensive treatment in an emergency room or at home for allergic bronchospasm; blood dyscrasias or convulsions that do not result in hospitalisation.)

For this trial, the following events are subjected to the same reporting requirement of SAE:

- Potential drug induced liver injury
- Pregnancy (See pregnancy section below for reporting pregnancies)
- Suspected transmission of an infectious agent via product (where required by the country specific legislation)

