## 12.6. Collecting and Recording AE and SAE

- All non-COVID-19 associated AEs and SAEs, whether or not they are related to the study intervention or protocol defined procedures must be documented in the patients' medical notes and eCRF. If no diagnosis is available, the Investigator should record each sign and symptom as individual AEs.
- The site will enter the AEs and SAEs into the eCRF as soon as it is known to the Investigator or sub investigator. The eCRF must be updated as soon as additional information is made available to the investor or sub investigator. If the electronic system is unavailable for more than 24 hours, then the site will use the paper form
- Reportable SAEs as defined above will be reported to the Co-Sponsor within 24 hours of the study team becoming aware of the event. SAE details will be included in the Safety Event Report Form (SERF) and the SERF emailed to [contact] or faxed to [name].
- The AEs and SAEs reporting period will be from participant consent until 28 days after randomisation.
- Pregnancy will be also subjected to the same reporting rules of SAE. Pregnancy details will be included in the SERF and the SERF emailed to [contact] or faxed to [name] within 24 hours of the study team becoming aware of the pregnancy.
- All AEs and SAEs will be followed up until resolved or the participant's participation in the study ends (i.e. until the final CRF is completed for that participant).
- When an AE/SAE occurs, it is the responsibility of the investigator or sub investigators to review all clinical information relating to the event.
  - The investigator or sub investigator will attempt diagnose the event based on direct examination and/or other clinical information.
  - The principle investigator must confirm within the SERF the causality assessment with the study drug. If the SAE is assessed as possibly related, probable related or definitely related, the principal investigator must also confirm the event expectedness versus the Reference safety information (refer to section 12.10).
- The Investigator must record follow-up information (related to the reported event) by updating the patient's medical records and the appropriate forms in the (e)CRF. The worst-case severity and seriousness of an event must be kept throughout the trial.

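### Adverse events enter the eCRF only if judged unrelated to COVID-19, a judgement made by implication by site staff who know the arm, so the AE/SAE comparison is open to differential attribution

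*Protocol*

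**What the plan says.** The condition appears in four places in the protocol's safety section, so it is not a slip in one sentence.

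- Section 12.1 sends to the notes and the eCRF "All Non-COVID-19 associated AEs and SAEs either observed by the research/clinical team, or reported to the research/clinical team".
- Section 12.2 defines an AE as "any non-COVID-19 related untoward medical occurrence, either newly acquired or worsening of a current AE". It repeats the restriction in three of its four qualifying bullets, including the one on abnormal laboratory results.
- Section 12.4 carries it into the SAE definition: "A serious non-COVID-19 associated adverse event is any untoward medical occurrence that at any dose".
- Section 12.6 states the collection rule: "All non-COVID-19 associated AEs and SAEs, whether or not they are related to the study intervention or protocol defined procedures must be documented". Relatedness to the drug is thus not a condition of entry, but unrelatedness to COVID-19 is.

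On who decides, section 12.6 says: "The investigator or sub investigator will attempt diagnose the event based on direct examination and/or other clinical information". Section 12.9 gives the causality assessment to the same people. Section 7 makes the trial open-label and section 8.7 returns the allocation at once to the person entering the data. Section 7 also lists what the trial is to investigate: "clinical effectiveness, safety, and resource utilisation".

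**The concern.** Several effects listed for favipiravir in section 9.6 can also occur in a patient hospitalised with COVID-19. The common ones include diarrhoea, raised liver enzymes and a reduced neutrophil count; the uncommon or rare ones include "Confusion; fulminant hepatitis; renal failure; agranulocytosis". When such an event occurs on standard care, COVID-19 is the obvious explanation and the event is not reportable. When it occurs on favipiravir, the drug is a second candidate and the event is more likely to be entered. The opposite error is also possible: a drug effect that looks like the disease is put down to the disease and never recorded.

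If either happens, the AE and SAE tables by arm mix event rates with attribution habits. The filter acts before data entry, so a clinical event left out of the eCRF cannot be restored by an analysis method. This is therefore a matter of what the protocol fixes, not of what it leaves to the SAP.

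**Working it through.** **1. Who makes the COVID-19 judgement.** No section says so in terms. Sections 12.6 and 12.9 give diagnosis and causality to the investigator or sub-investigator, and no other person, criterion or adjudication step is described. That the judgement is made with the arm known is an inference from these sections and the open-label design.

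**2. Fit with the protocol's own causality scale.** Section 12.9 has a grade, possibly related, for events with some indication of a drug cause that the participant's clinical condition could also explain. Here that condition will often be COVID-19. Such an event is a potential drug reaction, yet under 12.1, 12.2 and 12.6 it can be screened out before the scale is applied.

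**3. Whether later steps recover the event.** Under section 12.7.1 the Co-Sponsor assesses causality after receiving the SAE report. An event that was not reported does not reach that step.

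**4. What lies outside the filter.**
- Section 6.4 endpoints: all-cause in-hospital mortality, intensive care admission, ventilation, readmission, culture-confirmed infection.
- Section 10.2: "all routine data, including laboratory test results, procedures and medication will be collected as necessary". Section 9.4 adds blood count, liver function, and urea and electrolytes before randomisation and at day 5 to 10, plus day 14 to 28 for patients already discharged.
- Section 12.4: potential drug-induced liver injury takes SAE reporting without a COVID-19 qualifier. The drug-interaction bullet in 12.2 has none either. Both, however, need someone to suspect a drug.

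What remains exposed is mainly clinical AEs and SAEs without a laboratory or endpoint counterpart, such as confusion or diarrhoea.

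**5. Illustration of size.** The protocol states no figure on this point, so there is none to reproduce. Inputs: n = 250 per arm and alpha 0.05 (section 13.2), taken as two-sided because sidedness is not stated. The true event rates and attribution shares are assumptions. For scale, Appendix C Table 1 gives any-AE proportions in influenza of 227/894 = 25.4% on placebo and 419/1653 = 25.3% on favipiravir.

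Recorded rate = true rate × (1 − share attributed to COVID-19).

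P(significant) is the normal approximation for two proportions, with SE₀ = √(2p̄(1−p̄)/n) under the null and SE₁ = √((p₁(1−p₁)+p₂(1−p₂))/n) under the alternative.

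Main example, true 20% in both arms:
- Favipiravir, 30% attributed: 0.20 × 0.70 = 14%. Control, 50% attributed: 0.20 × 0.50 = 10%. Ratio 1.40.
- p̄ = 0.12, SE₀ = 0.0291, SE₁ = 0.0290, critical difference 1.96 × 0.0291 = 0.0570.
- P = 1 − Φ((0.0570 − 0.04)/0.0290) = 1 − Φ(0.585) = 0.28.

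| True rate, fav v control | Share attributed to COVID-19, fav v control | Recorded | Ratio | P(significant) |
|---|---|---|---|---|
| 20% v 20% | 50% v 50% | 10% v 10% | 1.00 | 5% |
| 20% v 20% | 30% v 50% | 14% v 10% | 1.40 | 28% |
| 20% v 20% | 30% v 60% | 14% v 8% | 1.75 | 57% |
| 16% v 10% | none | 16% v 10% | 1.60 | 51% |
| 16% v 10% | 30% v 50% | 11.2% v 5% | 2.24 | 72% |
| 16% v 10% | 50% v 30% | 8% v 7% | 1.14 | about 7% |

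The last row hides a true excess, but only because its shares run opposite to those in the rows showing over-recording. An equal filter does not bias the ratio but costs power: a true 35% v 25% has 68.5% power with full recording and 48.5% when 30% of events are dropped in each arm (24.5% v 17.5%).

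**The case against.** The restriction is stated four times and looks deliberate. In this population, deterioration from COVID-19 would generate many SAE reports that largely duplicate the section 6.4 endpoints. Much of the harm signal is also protected: liver, renal and neutrophil effects can be read from laboratory results, and section 16.1 has the DSMB consider the randomised evidence on mortality. Section 12.7 speaks of all safety events being recorded, and the scale in 12.9 has grades for events that the patient's condition explains, which suggests that ambiguous events are meant to be captured. The attribution shares have no source in the protocol, which also specifies no test of AE rates.

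Most of this stands as a limit on the point. A reader might infer that the whole safety comparison is lost and that no later analysis can help. The documents do not support that for laboratory harms or for the unfiltered endpoints. A reader might also infer that bias towards hiding harm is as likely as bias towards a false signal. The mechanism described above favours over-recording on favipiravir; masking is possible, but nothing in the protocol makes it equally likely.

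The objection does not remove the point. Section 12.7 does not define safety events or override the AE definition, and 12.9 grades only what has passed the earlier condition. The mortality endpoint covers in-hospital deaths only. Clinical events such as confusion have no unfiltered record assured by the protocol.

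**Conclusion.** The point holds in limited form. The protocol makes eCRF entry of AEs and SAEs depend on a COVID-19 judgement with no stated criteria and no blinded review, in an open-label trial that names safety as a purpose. The recorded AE/SAE comparison is therefore open to differential attribution, most plausibly over-recording on favipiravir relative to standard care. The size and direction of any bias cannot be derived from the documents. The figures show only that moderate differences in attribution (30% v 50%) could turn equal true rates into a nominally significant difference with probability about 28% at 250 per arm. The conclusion rests on the inference that unblinded site staff make the call. The exposure is mainly to clinical AEs and SAEs. Because part of the harm data is protected, this is something the sponsor should correct, not a defect that invalidates the trial.

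**What to change.** - In 12.1, 12.2, 12.4 and 12.6, require serious events and deaths to be entered in the eCRF in both arms whatever the cause, with COVID-19 relatedness (yes/no) as a data field and not a condition of entry. Leave expedited reporting on the Safety Event Report Form limited as it is now, so that the 24-hour workload does not grow.
- Compare ALT/AST, neutrophils and creatinine by arm (CTCAE grade and shift from baseline) from the routine results under 9.4 and 10.2, with no attribution step. This assumes that creatinine is part of the urea and electrolytes panel, since the protocol does not name it.
- Show the non-COVID-19 subset as a secondary display.

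The cost is protocol wording, one eCRF field and some extra entry of serious events at sites; the laboratory comparison uses data already collected. Non-serious clinical events would still pass through the filter. Section 3 gives 1 May 2020 as the actual start and this version is dated April 2021, so ascertainment would change mid-trial. Events before and after the change must be shown separately, or earlier serious events entered retrospectively from the medical notes.

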#### 9. STUDY INTERVENTIONS

A study intervention is defined as any investigational intervention(s) administered to a study participant in accordance study protocol.

For the trial medicinal supplies will be packaged and affixed with a label in accordance with regulatory requirements.

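### The adverse event definition in 12.2 depends on receiving an investigational intervention, which contradicts the arm-neutral collection rules and risks under-recording in the standard-care arm

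*Protocol*

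**What the plan says.** Section 9 of the protocol sets the term: "A study intervention is defined as any investigational intervention(s) administered to a study participant in accordance study protocol". Section 12.2 then uses it three times to say what counts as an AE:

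- the general definition covers an occurrence "in a patient or clinical trial participant administered a study intervention whether or not considered related to the study intervention";
- signs, symptoms and diseases must be "temporally associated with the use of a study intervention";
- new conditions count when "detected or diagnosed after the study intervention has been administered to the participant".

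Section 7 describes the control group as "Arm 2: Standard of care", with no investigational product, and gives the trial's purpose as "to investigate the clinical effectiveness, safety, and resource utilisation of early treatment intervention".

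The collection rules are framed differently. Section 12.6 states: "The AEs and SAEs reporting period will be from participant consent until 28 days after randomisation". Sections 12.1 and 12.6 require every AE and serious adverse event (SAE) not associated with COVID-19 to be recorded, regardless of relationship to the intervention. Section 10.3 collects both by telephone from participants discharged before day 10. None of these three sections mentions arm or dosing as a condition.

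**The concern.** The 12.2 wording suits a trial in which everyone takes the study drug. Here half the participants do not. A standard-care participant receives nothing investigational and has no administration time from which to date a new condition. A favipiravir participant has none until the first dose. A site that applies 12.2 to the letter would have no ground for entering an AE in either situation, while a site that follows 12.6 would enter both.

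Staff know the allocation, so drug-centred wording can lead to more complete recording in the favipiravir arm than in the control arm. Ordinary background events in hospital would then look like an excess on favipiravir, and the Data Safety Monitoring Board (DSMB), which assesses safety under 12.12 and 16.1, would see the same imbalance. This is separate from whether an event is judged to be COVID-19 related.

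**Working it through.** The protocol gives no figure on this point to reproduce. The check is mainly textual, followed by a short illustration.

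**Step 1: who can have an AE under the definition.**

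- Section 9: a study intervention is an investigational one.
- Section 12.2: an AE needs a participant who has been given a study intervention.
- Section 7: Arm 2 is given standard of care only.
- Result on plain wording: Arm 2 falls outside the general definition for the whole study, and Arm 1 falls outside it until the first dose.

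**Step 2: who has AEs collected under the other sections.**

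| Section | Rule | Does it need dosing? |
|---|---|---|
| 10.3 | Telephone collection of AEs and SAEs after discharge before day 10 | No |
| 12.1 | All non-COVID-19 AEs and SAEs that the team observes or is told of | No |
| 12.2, laboratory bullet | Results that have worsened since consent count | No |
| 12.4 | SAE definition has no administration condition, though it is phrased in terms of dose | Not explicitly |
| 12.6 | Window from consent to day 28 after randomisation | No |
| 12.9 | An event before dosing is the example of an unrelated AE/SAE | No; it presupposes an undosed participant |

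**Step 3: can both be followed?** No. The sections in step 2 presuppose AEs in people who have not been dosed, and the general definition in 12.2 excludes them. Section 12.2 also conflicts with itself, because its laboratory bullet counts from consent.

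**Step 4: size, as an illustration.** Inputs: 500 participants randomised 1:1 (section 8.1), so 250 per arm; any AE in 227 of 894 on placebo and 419 of 1653 on favipiravir (Appendix C, Table 1, pooled influenza studies).

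- Placebo: 227 / 894 = 25.4%. Favipiravir: 419 / 1653 = 25.3%.
- Difference: 25.35% − 25.39% = −0.04 percentage points. Standard error = √(0.2539 × 0.7461 / 894 + 0.2535 × 0.7465 / 1653) = 0.0181. The 95% interval is −0.04 ± 1.96 × 1.81, about −3.6 to 3.5 points.
- Controls with an AE outside the literal definition, if the placebo rate applied: 250 × 227 / 894 = 63.5, about 63.
- The same at assumed control risks of 10% and 50%: 250 × 0.10 = 25 and 250 × 0.50 = 125.
- If true rates were 25.4% in both arms and half of the control participants' AEs went unrecorded (an arbitrary fraction), the false excess on favipiravir would be 25.4 − 12.7 = 12.7 points.

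The pooled data show why the control rate matters: about a quarter of participants had an AE whether or not they took the drug, so an AE rate from one arm alone cannot be interpreted.

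**The case against.** The strongest reply is that the intent is clear and sites will follow it. The rules in 10.3, 12.1 and 12.6 apply to everyone, the window is tied to consent and randomisation, and 12.9 expects pre-dose events. This largely stands as evidence of intent. It does not remove the defect, because those sections say when and how to record an AE and rely on 12.2 for what an AE is. Nothing in the protocol says that collection is identical in the two arms.

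It can also be argued that standard of care is itself a study intervention: section 9.1 lists it beside favipiravir among the options to which participants are randomised, and 8.7 speaks of allocating an intervention to each participant. That reading is open, but section 9 says investigational, and standard of care is not that. An ambiguity of this kind is still a reason to clarify.

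A reader might go further and infer that the safety comparison has no control group, or that the tables will show about 63 favipiravir participants with AEs against none. The documents do not support either. The collection rules provide for control-arm AEs, and the SAE definition does not carry the administration condition. Deaths, intensive care, ventilation, readmission and culture-confirmed infection are endpoints in both arms (section 6.4). A count of zero would require every site to disregard 10.3, 12.1 and 12.6. Nor do the documents show that AE rates would be higher here than in the influenza studies, since the AE definition excludes COVID-19-related events.

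**Conclusion.** The point holds as an internal contradiction: sections 9 and 12.2 on one side, and 10.3, 12.1, 12.6 and 12.9 on the other. The consequence is a risk of unequal AE ascertainment between arms in an open-label trial, falling mainly on non-serious events in the control arm. It does not show that control-arm safety data will be absent.

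The documents do not fix the size of the bias. About 63 of 250 controls is the most that a literal reading could exclude if the pooled placebo rate of 25.4% applied (25 to 125 for assumed risks of 10% to 50%). Two assumptions carry that number: that influenza-trial rates transfer to this population, and that every site reads 12.2 literally. Neither is established, so it illustrates scale and is not a forecast. How AEs will be compared is a matter for the statistical analysis plan, which is not shown. The data feeding any such comparison, and the DSMB's review, depend on this definition.

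**What to change.** In 12.2, replace the three conditional phrases, "in a patient or clinical trial participant administered a study intervention whether or not considered related to the study intervention", "temporally associated with the use of a study intervention" and "detected or diagnosed after the study intervention has been administered to the participant", with wording that covers every participant in either arm, whether or not any study drug has been given, over the period already set in 12.6. Keep the statement that relatedness is not required. Add one sentence saying that AEs and SAEs are collected in the same way in both arms.

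Leave the 12.6 window as it is. Moving its start to randomisation is not needed. Leave the causality procedure unchanged as well: limiting it to favipiravir recipients would conflict with 12.1 and add a new procedural difference between arms.

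The cost is a few words in one section and a reminder to sites. The downside is some extra AE entry for standard-care participants at sites that had followed the literal definition.
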